**PROTOCOL**  
**HUMALOG® MIX50/50™ FOR THE TREATMENT OF INSULIN REQUIRING**  
**GESTATIONAL DIABETES**

**RATIONALE**

Controlling hyperglycemia during pregnancy decreases the risk of adverse neonatal and maternal outcomes. Not only must fasting glucose be normalized, but clinical evidence also indicates that controlling postprandial hyperglycemia will significantly reduce the risk of adverse neonatal and maternal outcomes (1-2).

Standard therapy to achieve near-normal glycemia in gestational diabetes involves combining intermediate-acting basal (NPH) insulin with rapid-acting insulin (insulin lispro), thereby requiring 6 daily injections (Figure 1). Premixed Humalog® Mix50/50™ has the potential advantage over combination rapid-acting plus NPH insulin because it involves fewer injections, and those injections are associated with mealtime (Figure 2). The potential downside to the premixed formulation is nocturnal hypoglycemia associated with the time lag between the dinner and breakfast dose. This study will evaluate the efficacy and safety of Humalog® Mix50/50™ compared to that of Humalog® plus Humulin N® insulin for the treatment of insulin-requiring patients with gestational diabetes mellitus, while monitoring glucose control, intrauterine growth and assessing pregnancy outcomes.

**PREVIOUS WORK**

The principal investigator has established nationally-recognized protocols for the care of pregnant women with diabetes (3-6) and has played an active role in the field of gestational diabetes (7-9). Thus she is uniquely positioned to study the potential efficacy of new therapies for gestational diabetes. Two studies have particular relevance to the proposed research and are attached to this application. [name] and colleagues studied the metabolic and immunologic effects of insulin lispro in gestational diabetes (10) by randomizing women to receive either regular human insulin or insulin lispro before consuming a test meal. The study proved the safety of insulin lispro for women with gestational diabetes. In a subsequent study led by Pettitt (11), postprandial glycemic control was demonstrated in women with gestational diabetes taking insulin aspart via higher insulin peak and lower demand on endogenous insulin secretion.

**STUDY HYPOTHESIS**

Humalog® Mix50/50™ administered as 3 injections daily is equivalent to Humalog® plus Humulin N® insulin administered as 6 separate injections daily in terms of glucose control, but may have some advantages due to increased ease of use.

**PRIMARY OBJECTIVE**

Compare the efficacy and safety of three daily injections of Humalog® Mix50/50™ to six daily injections of Humalog® and Humulin N® insulin, by fasting glucose measurements.

## **SECONDARY OBJECTIVES**

1. Compare incidence of maternal hypoglycemic events between the two treatment arms.
2. Compare neonatal outcomes between the two treatment arms.
3. Compare fetal fat measurements between the two treatment arms.
4. Compare adherence rates and patient acceptability of the two injection regimens
5. Compare A1C between groups at end of protocol and within groups at baseline versus end of protocol.

## **STUDY DESIGN**

Women diagnosed with gestational diabetes receive diet and exercise education. They are instructed to record their pre- and post-prandial glucose measurements obtained by fingerstick. Following one week of diet and exercise therapy, patients with fasting glucose levels >90 mg/dL or postprandial glucose level >120 mg/dL will be recruited to this study.

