### **Inclusion Criteria**

- Pregnant and at least 13 weeks gestation
- Diagnosed with gestational diabetes
- Failed diet therapy

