## **METHODS**

Subjects will be randomized 1:1 to receive usual insulin treatment of six injections daily (Humalog® injected three times daily before meals plus Humulin N® insulin injected at 8am, 4pm and midnight) as diagrammed in Figure 1, or 3 injections of Humalog® Mix50/50™ (injected only before meals) as diagrammed in Figure 2.

Baseline measures will include glucose tolerance test data, height, weight, and A1C by DCA2000+. In addition to the standard instruction to test blood glucose pre- and one-hour postprandial, all participants will be asked to test blood glucose levels at 3 a.m. Patients on the Humalog® Mix50/50™ arm of the study will be initially prescribed insulin doses of 0.3 times their weight in kilograms to be taken before each of three meals. Those on the standard therapy arm will be initially prescribed insulin doses calculated at 0.15 times their weight in kilograms for each of their 6 injections.

---

 We shall use American Diabetes Association criteria for diagnosis of GDM: blood glucose concentration >140 mg/dL one hour after administration of a 50 gram glucose load, followed by an oral glucose tolerance test (OGTT) in which 2 or more of the readings are at or above 95 mg/dL fasting, 180 mg/dL at one hour, 155 mg/dL at 2 hours and 145 mg/dL 3 hours after administration of a 100 gram glucose load (12).

Participants will be seen weekly for adjustment in dosages based on their food records, downloaded glucose monitor data and A1 C levels. Subjects in the study group whose fasting glucose exceeds 90 mg/dl will be prescribed Humalog® Mix75/25™ at their evening meal rather than Humalog® Mix50/50™. Subjects will be discontinued from the study if their 3 a.m. blood glucose concentration falls below 55 mg/dL that is unresponsive to a snack at bedtime or if their fasting blood glucose is greater than 90mg/dL despite increasing doses of Humalog® Mix50/50™ at the evening meal followed by treating with Humalog® Mix75/25™ at the evening meal.

Maternal weight will be recorded at each visit. Participants will be asked to bring their supply of insulin pens to every other visit, for which they will be paid ten dollars to maximize cooperation with this essential aspect of the research. The insulin pens will be counted as measures of adherence.

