## **PRIMARY EFFICACY MEASURES**

The primary measure used to substantiate the primary study objective will be maternal glucose control as reflected by fasting values from glucose monitor data.

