## **STATISTICAL ANALYSIS**

Data analysis will be done using SAS for Windows version 9. Differences between groups in continuous variables (glucose, A1C, birth weight etc.) will be compared with t-tests and potential confounders (age, race/ethnicity etc.) will be controlled for with linear regression. Differences in categorical variables (hypoglycemic events, macrosomia, type of delivery

etc.) will be evaluated using chi-square or Fisher's tests as appropriate. Our tests will be testing the hypothesis that the two treatments are different and the null hypothesis will be equivalence.

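### Women can enter on postprandial glucose alone, yet the primary comparison is on fasting glucose and does not name entry fasting level as a covariate

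*Protocol*

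**What the plan says.** Under Study Design, after a week of diet and exercise, "patients with fasting glucose levels >90 mg/dL or postprandial glucose level >120 mg/dL will be recruited to this study". The two thresholds are joined by *or*, so either is enough.

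Nothing else in the protocol closes the postprandial-only route. The inclusion criterion "Failed diet therapy" carries no fasting threshold. The diagnostic footnote in Methods asks for an OGTT in which "2 or more of the readings are at or above 95 mg/dL fasting, 180 mg/dL at one hour" and so on. Any two of the four readings will do, and fasting need not be one of them. The exclusion criteria do not mention glucose.

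The Primary Objective is judged on fasting measurements, and Primary Efficacy Measures defines the outcome as "maternal glucose control as reflected by fasting values from glucose monitor data". Methods uses the same 90 mg/dL figure as the level above which fasting glucose in the Mix50/50 arm calls for action.

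On allocation, Methods says "Subjects will be randomized 1:1 to receive usual insulin treatment of six injections daily" or three of the premix, and nothing more. Statistical Analysis compares continuous outcomes by t-test and provides linear regression for confounders. Age and race/ethnicity are the examples given, in an open list. Entry fasting glucose is not named.

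The Study Hypothesis is that the premix "is equivalent to Humalog® plus Humulin N® insulin administered as 6 separate injections daily in terms of glucose control". Statistical Analysis states: "Our tests will be testing the hypothesis that the two treatments are different and the null hypothesis will be equivalence".

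**The concern.** The entry rule and the primary outcome do not match. Some women are enrolled because of glucose after meals, while their fasting glucose already meets the protocol's own limit. All women are then compared on fasting glucose. Two consequences follow.

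- **Precision.** Women entering with fasting glucose above 90 mg/dL and women entering at or below it start from different levels of the variable that becomes the outcome. With 15 evaluable women per arm, an analysis that does not use the starting level leaves avoidable noise in the primary comparison.
- **Dilution.** If postprandial-only entrants have less room for their fasting glucose to differ between regimens, the average arm difference shrinks. In a trial meant to show superiority this would work against the hoped-for result. Here the hypothesis is equivalence and the test is for a difference, so a smaller average difference makes the hoped-for reading more likely.

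**Working it through.** **Inputs from the protocol (Sample Size).** 15 evaluable women per arm; difference 8 mg/dL; significance level 0.05 (taken as two-sided); power 80%. The SD is attributed to a population survey but not printed. The share of postprandial-only entrants, *f*, and their expected fasting difference are not given either, so ranges are assumed.

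**Step 1: the plan's own figure.** Without the SD, the 80% cannot be checked directly, only solved backwards. For a two-sample t-test with 28 degrees of freedom, the noncentrality is δ / (SD × √(2/15)). Setting δ = 8 and power = 0.80 gives SD = 7.55 mg/dL (variance 57.0). The normal approximation gives 7.82. The SD of 7.55 is used below, so the starting power is 80% by construction.

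**Step 2: dilution.** Let women entering with fasting glucose above 90 mg/dL have a true difference of 8, and let postprandial-only women keep a fraction *k* of it. The average difference is 8 × [1 − f(1 − k)]. The standard error is 7.55 × √(2/15) = 2.76.

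| Share postprandial-only (f) | Fraction kept (k) | Average difference (mg/dL) | Noncentrality | Power |
|---|---|---|---|---|
| 25% | 0 | 8 × 0.75 = 6.0 | 2.18 | 56% |
| 50% | 0 | 8 × 0.50 = 4.0 | 1.45 | 29% |
| 25% | 0.5 | 8 × 0.875 = 7.0 | 2.54 | 69% |
| 50% | 0.5 | 8 × 0.75 = 6.0 | 2.18 | 56% |
| any | 1 | 8.0 | 2.90 | 80% |

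These rows hold the SD fixed. With no effect in postprandial-only women, allowing for the extra spread from a mixed response in one arm lowers 56% to 52% and 29% to 26%.

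**Step 3: variance tied to entry route.** If half the women enter by each route and the routes differ by *g* mg/dL in mean on-study fasting glucose, the route accounts for a variance of 0.25 × g². For an assumed g = 10 this is 25, or 25/57.0 = 44% of the implied total. Adjustment could remove that part. How much of an entry gap survives weekly dose adjustment is unknown, so this is only an illustration. At g = 15 it would be 56.25 of 57.0, leaving almost no variation among women of the same route. A gap that large is not credible alongside the implied SD.

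**Step 4: what the raised-fasting stratum alone can show.** If half enter that way, about 7 and 8 women per arm remain. At SD 7.55, the standard error is 7.55 × √(1/7 + 1/8) = 3.91. With 13 degrees of freedom the 95% half-width is about 8.4 mg/dL, and power for 8 mg/dL is about 47%.

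**The case against.** The strongest reply is that every woman receives the full regimen of her arm, whatever her entry route. Methods gives the comparator a midnight intermediate-acting dose and the premix arm none, so the overnight contrast also reaches postprandial-only women. Their fasting values can diverge in either direction. This stands: a zero effect in these women is an assumption, and the last row of the Step 2 table is as open as the first two.

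These women also belong to the population in the title, and the average effect over all treated women is a legitimate target. That stands too. The point concerns how the analysis handles them, not whether they should be enrolled.

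A reader might draw four stronger inferences that the documents do not support:

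- *That the Rationale itself predicts worse fasting control on the premix.* The phrase "the time lag between the dinner and breakfast dose" is given there as a source of nocturnal hypoglycaemia, not of raised fasting glucose.
- *That the protocol specifies an unstratified list.* It states only 1:1 allocation. Details of stratification and the full covariate list may sit in a document not at hand, and the confounder list is open-ended. Silence on these is not in itself an error.
- *That chance imbalance in entry route is a further bias.* A gap of four women between arms of 15, with an assumed 10 to 15 mg/dL between routes, would shift the arm difference by 4/15 × 10 = 2.7 to 4/15 × 15 = 4.0 mg/dL. Under randomisation, such shifts are already in the t-test's standard error. They are a reason to adjust for precision, not an additional harm.
- *That equivalence should be claimed only if the raised-fasting stratum supports it.* Step 4 shows that the stratum is too small to carry such a condition, and the protocol gives no margin against which to judge support.

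**Conclusion.** The mismatch is in the text. Entry is possible on postprandial glucose alone, the primary outcome is fasting glucose, and the analysis section does not name the entry fasting value. The direction of any dilution also follows from the text, because equivalence is the hypothesis and no difference is the null.

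The size is not established. Depending on how much of the effect postprandial-only women keep, power at a 25% to 50% share ranges from 56% down to 29% (none), from 69% down to 56% (half), or stays at 80% (all). These figures rest on a two-sided test, the back-solved SD of about 7.5 mg/dL and an assumed share. One might read the entry rule as making a finding of equivalence a foregone conclusion. The protocol does not support that, since all women receive the regimen contrast. What remains is a worthwhile improvement to the analysis and the allocation. The lack of an equivalence margin is a separate and firmer problem, which this change does not cure.

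**What to change.** 1. Make the primary fasting comparison a linear regression on treatment arm with run-in fasting glucose as a covariate. Women already record fingerstick values during that week and entry depends on them, so no new measurement is needed.
2. Stratify the 1:1 randomisation by entry route: fasting glucose above 90 mg/dL (with or without a raised postprandial value) versus postprandial only.
3. Report the arm difference with its 95% interval in the raised-fasting stratum as a supportive analysis, not as a condition for the main conclusion.

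The cost is one regression term, one two-level stratum and no extra women or visits. The subgroup interval will be wide, about ±8.4 mg/dL if half the women enter by that route, and the report should say so. The entry criteria need not change.

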### **Inclusion Criteria**

- Pregnant and at least 13 weeks gestation
- Diagnosed with gestational diabetes
- Failed diet therapy

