### **Exclusion Criteria**

- pregnant women <18 years old or over 45 years old
- a urine dipstick urine with >2+ protein
- blood pressure >140/80 mmHg; hematocrit <30%
- refusal to take insulin
- inability to understand instructions or to consent to participate.

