Consent forms of enrolled patients will be given to the hospital at prenatal enrollment and will be part of their hospital medical chart at the time of delivery. Delivery room nurses will be instructed to collect cord blood and notify the study coordinator of the birth. Data collected from the birth will include sex of the baby, gestational week, ethnicity, length, birthweight and mode of delivery. Neonates will be assessed for macrosomia and hypoglycemia. Maternal postpartum glucose levels will be recorded.

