## **SECONDARY EFFICACY MEASURES**

The maternal A1C will be measured by Bayer DCA2000+ at baseline and at end of protocol. The 3 a.m. glucose records will be assessed for nocturnal hypoglycemia. Maternal weight gain will be assessed as an indicator of over-insulinization. In addition, we will analyze baby birth weight percentile, APGAR scores, cord blood insulin levels and mode of delivery as measures of fetal outcome. We will use insulin pen count data as an indicator of maternal adherence to the therapy regimen.

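### Time on treatment can vary widely because entry has no upper gestational limit, yet weight gain, A1C and neonatal outcomes are compared without regard to exposure

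*Protocol*

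**What the plan says.** The Inclusion Criteria set a floor, "Pregnant and at least 13 weeks gestation", and no ceiling. The Exclusion Criteria limit maternal age ("pregnant women <18 years old or over 45 years old"), proteinuria, blood pressure, hematocrit, refusal of insulin and ability to consent, but not gestation. Under Study Design, recruitment comes after diagnosis: "Following one week of diet and exercise therapy". No latest week is given. The Sample Size section does not define an evaluable subject by time on treatment.

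The measures concerned are secondary:

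- Weight: "Maternal weight gain will be assessed as an indicator of over-insulinization", with no period or scale stated. Methods provides for maternal weight at baseline and at each visit.
- A1C: "The maternal A1C will be measured by Bayer DCA2000+ at baseline and at end of protocol". Secondary Objectives adds: "Compare A1C between groups at end of protocol and within groups at baseline versus end of protocol". The end of protocol is not tied to a gestational week or to a minimum interval.
- Neonatal outcomes: birth weight percentile, APGAR scores, cord blood insulin and mode of delivery. Follow-up runs to birth: "Data collected from the birth will include sex of the baby, gestational week, ethnicity, length, birthweight and mode of delivery".

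Statistical Analysis compares continuous variables by t-test and categorical ones by chi-square or Fisher's test. Linear regression is to control for confounders; the list names age and race/ethnicity and is left open. Gestational week at entry and time on treatment are not named. Methods mentions 1:1 randomisation without stratification by gestation.

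**The concern.** All three groups of measures depend on how long a woman was treated. Weight gained on study grows with weeks on study whatever the insulin. A1C lags behind a change in glucose, so after a short exposure the final value still carries the pre-treatment level. Fetal growth before randomisation is part of birth weight in every woman, and a larger part in a late entrant.

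Three things are at stake. A raw weight gain may be read as over-insulinization when it mostly reflects weeks of follow-up. A true difference between regimens may be diluted, and similarity is the result the protocol anticipates. A fall in A1C within an arm may be credited to the regimen although it mixes treatment with advancing gestation and with recruitment of women whose glucose was high at entry.

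**Working it through.** The protocol gives no figure for exposure. Its one power statement (80% for 8 mg/dL in fasting glucose, 15 per group) concerns the primary measure and is not at issue here.

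**Inputs from the protocol:** entry from 13 weeks, no upper limit, one week of diet and exercise first, 15 evaluable women per arm.

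**Assumptions (not in the protocol):** treatment until delivery at 40 weeks; uniform entry over weeks 13 to 37; normal gain of 0.3 to 0.5 kg per week; A1C moving to its new level with a half-time of 4 weeks (range 3 to 5).

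**1. Exposure** = 40 − entry week.
- Entry at 13: 27 weeks. Entry at 28: 12 weeks. Entry at 37: 3 weeks.
- With delivery at 37 or 41 weeks, the longest exposure is 24 or 28 weeks.

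**2. Expected normal gain on study** = weeks × rate.
- 27 weeks: 27 × 0.3 to 27 × 0.5 = 8.1 to 13.5 kg.
- 3 weeks: 3 × 0.3 to 3 × 0.5 = 0.9 to 1.5 kg.

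**3. Spread from exposure alone.**
- SD of exposure = (37 − 13)/√12 = 6.9 weeks.
- In weight: 6.9 × 0.3 to 6.9 × 0.5 = 2.1 to 3.5 kg.

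**4. Chance imbalance between arms** = 1.96 × SD × √(2/15).
- Entry over weeks 13 to 37: 1.96 × 6.93 × 0.365 = 4.96, about 5 weeks, or 1.5 to 2.5 kg.
- Entry over the narrower weeks 24 to 36: SD = 12/√12 = 3.46; 1.96 × 3.46 × 0.365 = 2.5 weeks, or about 0.7 to 1.2 kg.

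**5. Share of the A1C effect visible** = 1 − 0.5^(weeks/half-time).
- 3 weeks: 1 − 0.5^(3/4) = 41% (34% to 50% for half-times of 5 and 3 weeks).
- 12 weeks: 1 − 0.5^(12/4) = 88% (81% to 94%).

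**6. Dilution, as an illustration.** Suppose an outcome would have 80% power with 15 per arm, and a share f of women enter too late to show any effect. Power is then Φ[(1 − f)(1.96 + 0.84) − 1.96].
- f = 10%: 71%. f = 20%: 61%. f = 30%: 50%.
- The protocol powers none of these secondary measures, so this shows the direction and rate of loss, not their actual power.

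**7. A route beyond chance.** In Methods, the fasting-glucose limb of the discontinuation rule is expressed only through the Mix50/50 and Mix75/25 steps. As written it can end participation in the Mix arm and has no counterpart in the six-injection arm. If gain is taken to the end of participation, the Mix arm's raw gain could be lower merely because follow-up was shorter. The protocol gives no expected discontinuation rate, so this effect cannot be sized.

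**The case against.** The strongest reply has four parts.

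- **Randomisation protects the comparison.** Variation in entry week is the same in both arms on average, and chance imbalance at 15 per arm applies to any prognostic factor. This stands. A reader might infer that open entry systematically biases the comparison; the 1:1 allocation does not support that. The one arm-specific route is the discontinuation rule, which acts after randomisation.
- **Late entrants still carry information.** A reader might infer that A1C, weight gain and birth weight cannot reflect the regimen in women who enter late. The illustration above shows 34% to 50% of the A1C effect after 3 weeks, so the effect is diluted by degree, not absent. Nor do weekly dose adjustments mark out late entrants: "Participants will be seen weekly for adjustment in dosages" applies to everyone throughout.
- **The analysis may already cover this.** The confounder list is open, the weights are collected, nothing says gain will be a raw total, and a separate analysis plan could settle the scale. This stands in part. But the protocol does state t-tests on these measures and names its leading confounders, and the one most closely tied to exposure is not among them. Likewise, nothing claims that a within-group fall in A1C proves an effect, but that comparison is a listed objective with no such caution.
- **Broad entry is a legitimate choice.** This also stands. Under the same uniform-entry assumption, requiring entry by week 32 (8 weeks before week 40) would exclude 5/24 = 21%, about 8 of 40 women, and would reduce the exposure SD only from 6.9 to 19/√12 = 5.5 weeks. The missing upper limit is therefore not in itself an error.

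**Conclusion.** The point holds as a weakness in how secondary measures are analysed. As written, time on treatment may range from about 3 to 27 weeks, and the stated comparisons ignore it. With 15 per arm, chance alone could put the arms about 5 weeks apart in mean exposure (1.5 to 2.5 kg) under uniform entry over weeks 13 to 37, or about 2.5 weeks (0.7 to 1.2 kg) if entry falls in weeks 24 to 36. Shorter follow-up under the Mix-arm discontinuation rule could add a difference of unknown size.

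These sizes rest on the assumed delivery week, entry distribution and weekly gain. Actual entry weeks are unknown, and the diagnostic sequence may narrow them in practice. Birth weight percentile may allow for gestation at delivery, but not for the length of treatment. A reader might extend the point to the trial's main conclusion; the documents do not support that, because the primary measure is fasting monitor glucose and the sample size rests on it.

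**What to change.** Change the analysis wording as follows:

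- Analyse maternal weight gain as kg per week from randomisation, using the weights recorded at each visit.
- Include gestational week at randomisation as a covariate for A1C (together with baseline A1C), for weight gain and for neonatal outcomes. Record it as a baseline measure; it has to be established for the eligibility check anyway. Do not use realised time on treatment as the covariate, since discontinuation can affect it after randomisation.
- Label the within-group A1C change as descriptive, so that only the between-arm comparison supports a conclusion.

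This needs a few lines of text and no new data beyond noting the gestational week. It has limits: a rate from a very short exposure is imprecise, adjustment cannot supply exposure that a late entrant never had, and a weekly rate removes the effect of shorter follow-up but not any selection in who is discontinued.

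An upper gestational limit or a stated minimum exposure is an optional design choice, to be weighed against recruiting 40 women in 12 months. It is not part of the required change.
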